9.3 Missing Data

The CISTO research team aims to maintain the highest level of participant involvement and survey completion; they have achieved over 90% completion rates over similar time periods in a prior study with a similar data collection burden.¹¹ Because missing data is always a possibility, the DCC will monitor missing data through automated nightly reports, making these available to staff at CISTO practice sites to correct missing data fields, if possible. These reports will also be used to create a plan to prevent missing data in the future a participant or practice site which previously provided incomplete data. Important data elements will be prospectively monitored to examine patterns or reasons for “missingness”.

As a part of treatment effect estimation, the TMLE algorithm provides an integrated approach to incorporating uncertainty that arises due to missing longitudinal data. The mean outcome conditional on observing the outcome may be a biased estimate when missingness is informative. TMLE can reduce this bias when missingness is a function of measured baseline demographic and clinical characteristics. Missing outcome measurements will be accounted for by nonparametrically estimating the missing data mechanism to produce a matrix of missing data probabilities conditioned on baseline demographic and clinical characteristics. The missing data conditional probabilities will then be incorporated into the TMLE estimation procedure during the third step of updating potential outcomes.¹³

When missing data are suspected to be *missing not at random*, any standard analysis of the available cases is likely biased. The bias cannot be corrected since missingness depends on unobserved data and therefore cannot be empirically modelled reliably. We will therefore assess the sensitivity of inferences made from missing data by imputing missing data under both pessimistic and optimistic scenarios and repeating the TMLE algorithm to provide bounds on the statistical uncertainty. The characteristics of non-responders will be summarized in our final report and we will present the heterogeneity of the treatment effect due to missing data.

9.4 Sample Size and Statistical Power

We aim to recruit from a heterogeneous patient population that will allow for rich and broadly applicable estimation of outcomes and experiences after NMIBC that recurs after first-line BCG. **We will enroll up to 900 participants across a broad geographic recruitment area.** This cohort would represent the largest pragmatic study of recurrent high-grade NMIBC patients to date. The total sample size for CISTO is primarily motivated by statistical power considerations for **Aim 1**, comparing QOL between patients treated with medical management versus radical cystectomy. Presently, there are no guiding documents

on directly using TMLE in the calculation of statistical power for designing an observational study. The variance of the treatment effect estimate—and thus power—is a complicated function of the number treated in each group, the potential and observed outcomes, and the covariate-based probabilities of treatment with radical cystectomy. The 2:1 recruitment ratio of medical management to radical cystectomy patients at each CISTO site will ensure at least a 33% rate of radical cystectomy in the CISTO study population. However, based on actual rates of enrollment of cystectomy patients, we motivated the study sample size of 572 using 40.9% cystectomy patients in a standard two-sample repeated measures approach that will be less efficient than the analytic methods used at the time of data analysis.

Statistical power was fixed at 0.80 throughout and we considered two-sided tests with alpha=0.05 indicating statistical significance, with no adjustment for multiple comparisons for the primary question of interest. Correlation between repeated measures was assumed to be 0.3, an estimate we have observed in numerous other QOL studies. Minimal detectable effect sizes (units of QOL standard deviation) are reported in **Table 3** below for Aim 1 within subgroups with varying prevalence.

Table 3. Minimal Detectable Effect Sizes

		Subgroups		
		50%	30%	20%
Aim 1: Patient QOL	Overall	0.24	0.34	0.44

Aim 2 is largely descriptive in nature and no statements of statistical power were considered. With recruitment of 572 patient participants, anticipating 235 radical cystectomy patients and 337 patients treated with medical management in Aim 1 and conservatively allowing for 10% missing data, this study has >0.80 statistical power to detect small differences in QOL between treatment approaches (Cohen's $d = 0.24$)²⁰ that are well below the minimally important difference of 0.5. Assuming a similar balance of treatments within subgroups, this study has >0.80 power to detect moderate but clinically important effect sizes (Cohen's $d = 0.43$) within subgroups as small as 30% of the study cohort. From SEER, large treatment effect differences would be detectable in subgroups of gender (20% female), age (52% over 75), comorbid health conditions (22% Charlson Index 1 or greater), and CIS (25%). We will plan a subgroup analysis for patients receiving investigational agents as part of a phase III clinical trial if at least 10% of participants in the medical management arm are in a trial. To inform power calculations for our secondary outcomes of bladder cancer-specific mortality, we used data from a microsimulation model demonstrating low anticipated 1-year mortality event rates (0.8% for radical cystectomy, 3.6% for continued medical management). We would have 69% power to detect a similar difference in one-year mortality due to bladder cancer and 80% power to evaluate the difference between study arms in 2-year bladder cancer-specific mortality.

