## 6. Sample Size and Accrual

With recruitment of 572 participants, this study has  $>0.80$  statistical power to detect small differences in QOL between treatment approaches (Cohen's  $d = 0.24$ , or 5.5 points on the physical function scale of EORTC-QLQ-C30). Power analyses conservatively allowed for 10% missing data and assumed a correlation between repeated QOL measurements of 0.3. Assuming a similar balance of treatments within subgroups, this study also has  $>0.80$  power to detect moderate but clinically important treatment effects (Cohen's  $d = 0.43$ , or 9.9 points on the physical function scale of EORTC-QLQ-C30) within subgroups as small as 30% of the study cohort. Anticipated subgroups of this size include patients aged 75 years or older, women, and patients with multiple comorbid health conditions. For the secondary outcome of bladder cancer-specific mortality, data from a review combining multiple trials demonstrated an anticipated 1-year bladder cancer-specific mortality rate of 4.8% when treated with medical management. Assuming a 4.8% mortality rate in the medical management arm, this study has power to detect differences in 1-year bladder cancer-specific mortality rates of  $\leq 1\%$  in the radical cystectomy arm (power  $> 80\%$ ).

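### Claimed power above 0.80 for d = 0.43 in a 30% subgroup is about 0.78 on the stated inputs, and SAP 6 applies it to subgroups nearer 20%, where the detectable effect is about 0.54

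*Protocol*

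**What the plan says.** Protocol 9.4 bases power on a simple two-group comparison: "we motivated the study sample size of 572 using 40.9% cystectomy patients in a standard two-sample repeated measures approach". "Statistical power was fixed at 0.80 throughout", and "we considered two-sided tests with alpha=0.05 indicating statistical significance". The correlation between repeated measures is taken as 0.3. The arm sizes are given as "anticipating 235 radical cystectomy patients and 337 patients treated with medical management in Aim 1", "conservatively allowing for 10% missing data".

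From these inputs the protocol text states a detectable effect of d = 0.24 for the whole cohort, against a minimally important difference of 0.5. It states d = 0.43 at more than 0.80 power "within subgroups as small as 30% of the study cohort", assuming the same treatment balance within subgroups. It then gives SEER prevalences that include 20% female and 22% with a Charlson index of 1 or more, and says that large effects would be detectable in such groups.

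Table 3 covers the same ground: "Minimal detectable effect sizes (units of QOL standard deviation) are reported in" it by subgroup prevalence. In the text as converted from PDF, the headings are 50%, 30% and 20%, the values are 0.24, 0.34 and 0.44, and the word Overall sits in the cell before the values.

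SAP 6 repeats both effects and converts them to points: 5.5 for 0.24, and for 0.43, "or 9.9 points on the physical function scale of EORTC-QLQ-C30". It names patients aged 75 or older, women, and patients with multiple comorbidities as expected subgroups of the 30% size. SAP 4.1.1 plans a subgroup analysis by gender.

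**The concern.** The protocol text and the SAP give 0.43 for a 30% subgroup. Table 3 does not contain that value: it has 0.34 under the 30% heading, or 0.44 if the row is read as starting with the whole cohort. The stated inputs also do not quite give power above 0.80 at 0.43.

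More is at stake below 30%. SAP 6 attaches its 0.43 statement to women and comorbid patients, whom the protocol expects to make up about a fifth of the cohort. If the detectable effect there is above 0.5 SD, a null result in women could not be read as excluding a difference that the protocol itself calls important. A reader relying on 0.43 would think that it could.

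**Working it through.** **Inputs.** From Protocol 9.4: 235 and 337 patients, 10% missing, correlation 0.3, two-sided alpha 0.05, power 0.80, same treatment balance in subgroups. The documents do not state the variance formula. I take a baseline-adjusted comparison at one time point, with variance factor v = 1 - 0.3² = 0.91 in SD units. This is an assumption.

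**Formulas.** For subgroup prevalence f:
- n1 = 0.9 × 235 × f and n2 = 0.9 × 337 × f
- SE = √(v × (1/n1 + 1/n2))
- detectable effect = (1.960 + 0.842) × SE
- power at d = Φ(d/SE - 1.960)

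Noncentral t results are given alongside.

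**Step 1: reproduce the plan's overall figure.** n1 = 211.5, n2 = 303.3, SE = √(0.91 × (1/211.5 + 1/303.3)) = 0.0855. The detectable effect is 0.239 (t: 0.240), and power at 0.24 is 0.802 (t: 0.800). The stated 0.24 is recovered, which is the reason for using v = 0.91.

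**Step 2: the 30% subgroup.** n1 = 63.45, n2 = 90.99, SE = 0.1560. The detectable effect is 0.437 (t: 0.440). Power at 0.43 is Φ(0.43/0.1560 - 1.960) = 0.787 (t: 0.782). Power at 0.44 is 0.805 (t: 0.800).

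**Step 3: the 20% subgroup.** n1 = 42.30, n2 = 60.66, SE = 0.1911. The detectable effect is 0.535 (t: 0.541). Power at 0.43 is Φ(0.43/0.1911 - 1.960) = 0.614 (t: 0.606). Power at the minimally important difference of 0.5 is about 0.74. At 22%, scaling gives 0.541 × √(0.20/0.22) = 0.516, also above 0.5.

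**Step 4: sensitivity to the unstated formula** (noncentral t).

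| Variance factor | Loss | Power at 0.24, overall | Power at 0.43, 30% | Detectable effect, 20% |
|---|---|---|---|---|
| 0.91 | 10% | 0.800 | 0.782 | 0.541 |
| 1 | 10% | 0.762 | 0.743 | 0.567 |
| 1 | none | 0.805 | 0.787 | 0.537 |
| 0.91 | none | 0.840 | 0.823 | 0.512 |

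Only the last row exceeds 0.80 at 0.43. It omits the stated loss, and its overall detectable effect is 0.227 rather than 0.24. Averaging four follow-ups would give far more power, but its overall detectable effect would be 0.173, so it is not the stated basis either.

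**Step 5: Table 3, without any variance formula.** With power and treatment balance fixed, the detectable effect scales as 1/√f. The printed ratios are 0.34/0.24 = 1.417 and 0.44/0.24 = 1.833. A row for whole cohort, 50% and 30% needs √(1/0.5) = 1.414 and √(1/0.3) = 1.826. A row for 50%, 30% and 20% needs √(0.5/0.3) = 1.291 and √(0.5/0.2) = 1.581. The values therefore fit whole cohort, 50% and 30%, and the 20% value is absent from the converted text.

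**Step 6: points on the scale.** SAP 6 implies an SD of 5.5/0.24 = 22.9 or 9.9/0.43 = 23.0. So 0.44 is about 10.1 points and 0.54 is about 12.4 points.

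**The case against.** **The table may be sound.** A reader might infer that the plan contradicts itself at 30%, with 0.34 in Table 3 and 0.43 in the text, and that the table promises 0.80 power where the design has 0.5 to 0.6. The documents do not support this. If a heading for the whole-cohort column slipped into the data row during conversion, the values would shift by one column and the last could be lost. The ratios fit that explanation, and the text confirms 0.24 as the whole-cohort effect. Nothing can be charged to the plan on this count until the original page is seen.

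**The 0.43 figure is nearly right.** It would also be too strong to say that the design fails to deliver 0.43. The shortfall is 0.01 SD, or about 0.2 points (9.9 against 10.1). Because the formula is unstated, 0.44 is not the only defensible value: with v = 1, no loss and the normal approximation, the detectable effect is 0.4347, which rounds to 0.43. The protocol also says that its simple approach is less efficient than the planned analysis. That is a fair qualifier, but no gain is quantified, and the claim of power above 0.80 is stated for the simple approach with 10% loss.

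**The protocol is cautious about small subgroups.** For the SEER groups it claims only that large effects are detectable, which is consistent with 0.54. This stands for the protocol text. It does not cover SAP 6, which lists women and comorbid patients under the 30% figure and gives no prevalence of its own. The SAP may expect a different case mix, and its comorbidity definition need not match the Charlson cut-off, but it says neither.

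**Conclusion.** The point holds in a limited form and is minor. On the inputs that reproduce the plan's overall 0.24, power at d = 0.43 in a 30% subgroup is about 0.78, not above 0.80, and the detectable effect is 0.44. With the 10% loss and no baseline adjustment, power is about 0.74. The first gap is close to rounding and changes no decision.

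The more consequential part is the size of the subgroups named in SAP 6. At the protocol's own 20% for women, the detectable effect is about 0.54, with a range of 0.51 to 0.57 over the four variance and loss combinations tabulated. All of these exceed 0.5. Power for 0.43 there is about 0.61.

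These figures assume v = 0.91, the SEER prevalences and the same treatment balance in every subgroup. Whether Table 3 is really misaligned and lacks its 20% value remains open until the original page is checked.

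**What to change.** - Check Table 3 against the original page. It should read whole cohort 0.24, 50% 0.34, 30% 0.44, 20% 0.54. Supply the last value if it is missing there.
- State in Protocol 9.4 the variance formula and how the correlation of 0.3 and the 10% loss enter it. If the formula differs from the one assumed here, recompute the four values from it.
- Otherwise change 0.43 (9.9 points) to 0.44 (about 10.1 points) in Protocol 9.4 and SAP 6.
- In SAP 6, separate the subgroups by expected prevalence. Quote about 0.54 (about 12.4 points) for those near 20%, such as women, or give the prevalence that justifies treating them as 30% groups.

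The cost is wording only. Sample size, design and analysis are unchanged, and the stated subgroup figures become slightly less favourable.

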5.0 Study Design

5.1 Study Overview

CISTO is a prospective, non-randomized, observational cohort study of people with NMIBC that has recurred after intravesical BCG treatment. We will compare patients who choose medical management such as BCG, chemotherapy, or investigational therapies, with patients undergoing radical cystectomy.

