treatment effect of radical cystectomy through the creation of *potential outcomes*: two predicted outcomes for each individual patient participant, under the hypothetical assumption that they had been treated with either radical cystectomy or medical management. Next, similar to a propensity score approach, TMLE estimates the probability of treatment with radical cystectomy using either logistic regression, machine learning (LASSO, regression trees, etc.) or super learning approaches.¹⁶ In the third step of the TMLE approach, we use the probabilities obtained in the second step to update the initial estimate of each patient participant's pair of potential outcomes under each treatment group. Specifically, we will generate *targeted* estimates of the potential outcomes with regression models that incorporate both the initial potential outcome estimates and the probability of being treated with radical cystectomy. The average treatment effect is the mean difference between the updated potential outcomes and is interpreted as the causal difference in QOL if all patients had been treated with medical management versus having been treated with radical cystectomy.¹⁶ Because each patient has a pair of potential outcomes under each treatment, subgroup analyses are straightforward. As a secondary sensitivity analysis, we will evaluate these data using propensity score and G-computation methods. As a doubly robust and more efficient analytic approach relative to the comparative secondary approaches, we will use TMLE for presentation of the primary results for this study.

Longitudinal trajectories of the effect of treatment on patient QOL over time will be modeled and characterized using standard linear mixed effects models (primary analysis) or generalized estimating equations (GEE, secondary analysis). We will include covariates in the longitudinal data model to provide treatment effect estimates for subgroups of interest such as those defined by age, comorbidity, caregiver status, tumor severity, and use of investigational agents. For assessment of time-to-event outcomes (e.g., survival), we will use an extension of the TMLE approach appropriate for survival data.¹⁷

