## 1. General Design Considerations

### 1.1 Aims and Hypotheses

**Aim 1:** To compare patient-reported and patient-centered clinical outcomes between patients undergoing radical cystectomy and those receiving bladder-sparing therapies (BST) for NMIBC that have failed first-line BCG.

*Hypothesis 1.1: Patients undergoing radical cystectomy will have worse generic health-related QOL within 12 months of bladder removal surgery compared with BST patients.*

*Hypothesis 1.2: 12-month disease-free survival and metastasis-free survival will be better among radical cystectomy patients than among BST patients.*

*Hypothesis 1.3: Patient-reported and clinical outcome differences will vary within important subgroups including women, non-white patients, elderly patients, patients with multiple comorbid health conditions, patients with poor urinary function scores at the time of BCG failure, patients without caregivers, patients with atypical cancer histologies, and patients receiving investigational agents.*

**Aim 2:** To characterize the heterogeneity of treatments received and corresponding patient and caregiver preferences for NMIBC that have failed first-line BCG.

*Hypothesis 2.1: Patients who choose radical cystectomy for NMIBC with BCG failure will do so more often because they feel this offers their best chance for survival. Patients who choose BST will do so more often because they are concerned about the complications and QOL detriments associated with radical cystectomy.*

*Hypothesis 2.2: Patient and caregiver preferences will correlate strongly with observed treatments received and health-related QOL outcomes. We anticipate that QOL will vary by concordance of treatments received with treatment preferences and health state utilities.*

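### Receipt of an investigational agent is a form of medical management, so it cannot serve as a subgroup or covariate with its own cystectomy-versus-medical-management effect

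*Protocol*

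**What the plan says.** Protocol 5.1 defines the comparison: "We will compare patients who choose medical management such as BCG, chemotherapy, or investigational therapies, with patients undergoing radical cystectomy". Investigational therapy therefore sits inside one arm.

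Hypothesis 1.3, worded alike in Protocol 3.0 and SAP 1.1, expects outcome differences to vary within a list of subgroups. The list runs through sex, race, age, comorbidity, urinary function and caregiver status and ends with "patients with atypical cancer histologies, and patients receiving investigational agents".

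Protocol 9.2 says covariates will be put into the longitudinal model to give treatment effects by subgroup. Its list closes with "tumor severity, and use of investigational agents". The same section calls subgroup analysis straightforward under TMLE because each patient has a predicted outcome under both treatments.

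Protocol 9.4 adds "We will plan a subgroup analysis for patients receiving investigational agents as part of a phase III clinical trial", conditional on trial participants making up at least 10% of the medical-management arm. It gives no cystectomy count and names no comparator.

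SAP 4.1.1 lists four subgroups (age, gender, caregiver, carcinoma in situ). Investigational agents are not among them, and no reason is given.

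**The concern.** Every other item in Hypothesis 1.3 is a characteristic that a patient in either arm can have before treatment. Receipt of an investigational agent is different: it is a version of one of the two treatments being compared. Asking how cystectomy compares with medical management among agent recipients requires cystectomy patients who are agent recipients, and the documents define the group only through the medical-management arm.

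The risk is practical. A mixed model with the interaction would have the term dropped, or estimated from a handful of stray patients. A TMLE with agent use among its covariates could still return a number, but the cystectomy half would be extrapolated from patients outside the subgroup. Either result could be reported as heterogeneity of the treatment effect, which it would not be.

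**Working it through.** **Identification.** Let A = 1 for cystectomy and 0 for medical management, and S = 1 for receipt of an investigational agent.

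- Longitudinal model: mean = b0 + b1·A + b2·S + b3·A·S + other covariates. If S = 1 occurs only when A = 0, the column A·S is zero for everyone and b3 cannot be estimated. Without the interaction, b2 compares agent recipients with other medical-management patients, and b1 becomes cystectomy against medical management without agents. Neither is an effect within the subgroup.
- TMLE with S in the adjustment set: P(A = 1 | S = 1, baseline covariates) = 0, so positivity fails.
- TMLE with S left out, averaging the predicted pairs over patients with S = 1: a number results, and overlap on baseline covariates may be adequate. But the medical-management prediction is then drawn from all forms of medical management, so it does not isolate the agents.
- Agent recipients' own outcomes against cystectomy patients weighted to the recipients' baseline covariates: estimable, as an effect among those treated, if measured covariates suffice for confounding and overlap. Neither document specifies this.

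**Inputs (all Protocol 9.4).** "Statistical power was fixed at 0.80 throughout and we considered two-sided tests with alpha=0.05"; "Correlation between repeated measures was assumed to be 0.3"; "anticipating 235 radical cystectomy patients and 337 patients treated with medical management in Aim 1"; "conservatively allowing for 10% missing data". The minimally important difference is given as 0.5 SD.

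**Formula.** Detectable difference in SD units = (1.960 + 0.842) × k × sqrt(1/n1 + 1/n2). The factor k depends on the outcome model, which the documents do not fully state. With r = 0.3, k = sqrt(1 − 0.3²) = sqrt(0.91) = 0.954 for baseline adjustment, k = 1 unadjusted, and k = sqrt(2 × (1 − 0.3)) = 1.183 for a change score.

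**Reproducing the plan's figure.** n1 = 0.9 × 235 = 211.5 and n2 = 0.9 × 337 = 303.3. Then 2.802 × sqrt(1/211.5 + 1/303.3) = 0.251 unadjusted, 0.239 with baseline adjustment and 0.297 for a change score. Baseline adjustment matches the stated 0.24, so I take it as the working assumption. It is inferred, not stated.

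**Size of the subgroup at the trigger.** 0.10 × 337 = 33.7, about 34 patients, or 34/572 = 5.9% of the cohort. The subgroup power statement in Protocol 9.4 assumes the same treatment balance as overall. That would put 34 × 235/337 = about 24 cystectomy patients beside the 34, with a detectable difference of 0.75 SD. With none, 1/n1 is undefined and so is the detectable difference.

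**Could crossovers fill the cell?** Protocol 9.1 expects all or almost all cystectomy choosers to have surgery by 12 months. Suppose 0 to 5% of the 235 switch and 10% of those enter a trial (both assumed): 235 × 0.05 × 0.10 = 1.2 patients at most. Even 1 to 5 such patients would give a detectable difference of about 2.9 to 1.3 SD with baseline adjustment.

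**The contrast that can be estimated: agent recipients against all cystectomy patients** (10% missing, before any loss from weighting):

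| Share of medical-management arm | Recipients | Baseline-adjusted | Unadjusted | Change score |
|---|---|---|---|---|
| 10% (trigger) | 33.7 | 0.52 | 0.54 | 0.64 |
| 20% (assumed) | 67.4 | 0.39 | – | – |
| 30% (assumed) | 101.1 | 0.34 | – | – |

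For the first row: 2.802 × sqrt(1/211.5 + 1/30.33) = 0.544; × 0.954 = 0.519; × 1.183 = 0.644. If weighting halved the effective cystectomy sample (illustrative), the baseline-adjusted 0.52 would become about 0.55.

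**The case against.** The best defence has four parts.

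- The sentence in Protocol 9.4 names no comparator, estimand or interaction. Its trigger, a share of the medical-management arm, suggests that the authors knew where these patients sit. This stands for that sentence alone. The cystectomy-versus-medical-management reading comes from Hypothesis 1.3 and Protocol 9.2; if another contrast was meant, it is not written down.
- SAP 4.1.1 does not include the subgroup, so the SAP as written fits no such term. This also stands, and it limits the likely harm. But SAP 1.1 keeps the hypothesis, Protocol 9.2 and 9.4 keep the analysis, and neither document says which prevails. The SAP list also omits race, comorbidity, urinary function and histology, so its omission of agents cannot be read as a deliberate correction.
- A reader might infer that nothing can be estimated for these patients. The documents do not support that. An effect among those treated is available if agent use stays out of the adjustment set. What fails is the effect conditional on agent use.
- A reader might also take the number of cystectomy patients in the subgroup to be exactly zero. No text bars a patient who chose cystectomy from a later trial, and arms follow the choice at enrollment (Protocol 9.1). The supportable statement is that there would be essentially none, and too few to help.

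**Conclusion.** The point holds for the wording of Hypothesis 1.3 in both documents and for Protocol 9.2 and 9.4. Agent use is part of the medical-management treatment, and as a covariate interaction or TMLE adjustment variable it leaves the within-subgroup effect unidentified. This rests on the Protocol's own arm definition and trigger, and on negligible crossover from cystectomy into a trial.

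The consequences are bounded. The analysis is conditional and concerns one subgroup. Nothing here supports inferring that the primary endpoint or the main TMLE comparison is compromised. Nor does limited precision prove non-identification; that is a separate matter. For the contrast that can be estimated, the detectable difference at the minimum trigger is 0.52 to 0.64 SD, depending on an unstated variance model. That is slightly to moderately above the Protocol's 0.5, and with baseline adjustment it falls below 0.5 if the share reaches 20% or 30%.

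**What to change.** 1. Remove receipt of investigational agents from Hypothesis 1.3 (Protocol 3.0 and SAP 1.1) and from the subgroup covariates in Protocol 9.2.
2. Align Protocol 9.4 with the SAP. If the 10% trigger is kept, both documents should name the analysis that follows:
   - (a) agent recipients against cystectomy patients weighted to the recipients' baseline covariates, with agent use not a model covariate, labelled an effect among those treated and not effect heterogeneity;
   - (b) the primary TMLE repeated without these patients, as a sensitivity analysis.
3. State who counts. The trigger counts patients in a trial, while the analysis concerns those receiving an agent; if some trial participants receive a comparator, the group at the trigger is smaller than 34.
4. Report the precision of (a) with its variance assumption and the effective sample size after weighting.

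The cost is wording and a small amount of extra analysis, with no new data. The downside is that a named subgroup hypothesis is replaced by a separate contrast.
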